### **1.3. Data Format**

Data will be transmitted electronically for analysis in either Excel/CSV or SAS datasets. All files will be archived onto the computer system where the analysis will be performed. A working copy of these files will be created for analysis. Each file will be scanned for viruses, successfully opened, and content confirmed. Any electronic record issues will be reported to the provider.

### **1.4. Data Analysis Methods**

#### **1.4.1. General Methods**

Analyses will be conducted using SAS version 9.4 or higher or R version 4.1.2 or later. Tabulations will summarize for the immunogenicity parameter over time and treatment group for data collected during the dose escalation phase, and by dose and tumor type for the expansion phase.

For categorical variables, summary tabulations of the number and percentage of patients within each category (with a category for missing data) of the parameter will be presented. For continuous variables, the number of patients, mean, median, standard deviation (SD), minimum, and maximum values will be presented. In addition, geometric mean and % CV will be presented. Summary statistics will be presented, as well as confidence intervals (CIs) on selected parameters, as described in the sections below. Tables will display dose cohorts in the column headings.

This study is primarily descriptive in nature; therefore, formal statistical hypothesis testing will be limited. Data will be presented by patient in data listings and summarized by dose cohort.

All output will be incorporated into Microsoft Word or Excel files, or Adobe Acrobat PDF files, sorted and labeled according to the International Conference on Harmonisation (ICH) recommendations, and formatted to the appropriate page size(s).

Except if noted, listings will be presented by dose cohort. Within each dose cohort, patients will be ordered by patient ID number, mutation (mKRAS / mNRAS) and within each patient, the data will be ordered by ordinal visit / week.

### **1.5. Population Definitions**

The following patient populations will be evaluated and used for presentation and analysis of the immunogenicity or ctDNA biomarker data:

- Immunogenicity Population: All patients who receive any amount of study treatment and contribute any immunogenicity data.
- ctDNA Population: All patients who receive any amount of study treatment and contribute any ctDNA data.

### **1.6. Baseline Definitions**

For all analyses, baseline will be defined as the most recent measurement prior to the first administration of study drug. For immunogenicity analyses, this will be the sample collected on Visit 2. For ctDNA, this will be the sample collected at Visit 3. If results are missing at Visit 3 but available for Visit 2, Visit 2 results may be used as baseline.

**1.7. Multiple Comparisons/Multiplicity**

No adjustments for multiplicity will be made in a study with a descriptive interpretation.

**1.8. Timing of Analyses**

Analyses will occur after the completion of each cohort including completion of immunologic and ctDNA assays.

**1.9. Missing, Unused, and Spurious Data**

In general, there will be no substitutions made to accommodate missing data points.

For all assays, the limit of quantification (LOQ) will be used if available.

## **2. STUDY ANALYSES**

### **2.1. Immunogenicity Analysis**

Cellular responses will be characterized by:

- Ex vivo Intracellular cytokine staining
- In Vitro stimulated Intracellular cytokine staining
- Ex vivo Fluorospot
- In vitro stimulated Fluorospot
- Ex vivo Dextramer
- In vitro stimulated Dextramer

Response will be determined in two ways

- Method 1 – For subjects who are negative (below the limit of quantification) at baseline and have a detectable post baseline value (above the limit of quantification) will be considered a responder. For subjects who have detectable baseline values, a two-fold increase from baseline will be considered a responder.
- Method 2 (Fluorospot only)– distribution free resampling (DFR) will be applied using the methods described by Moodie et al 2010. A minimum threshold value of 2-fold difference between control and experimental wells will be assessed.

#### **2.1.1. Intracellular Cytokine Staining**

Actual and increase from baseline values for ex vivo and in vitro stimulated (IVS) Intracellular Cytokine (ICS) staining results will be presented at each timepoint by dose level and antigen. In addition to each cytokine, the sum of CD4 and CD8 cytokines will be summed and summarized with descriptive statistics. Non-stimulated (NS) results will be included in data listings but not tabulated.

Listings will include actual value and absolute and fold-change from baseline.

#### **2.1.2. Fluorospot**

Actual and increase from baseline values for ex Vivo and in vitro stimulated (IVS) Fluorospot (FS) results will be presented at each timepoint by dose level, assay, and antigen. In addition, the sum of results (IFN $\gamma$ , Granzyme B, and IFN $\gamma$ +Granzyme B for Ex vivo FS and IFN $\gamma$ , TNF $\alpha$ , IFN $\gamma$ +TNF $\alpha$  for IVS) will be calculated for each antigen. Non-stimulated (NS) results will be included in data listings but not tabulated.

Ex vivo (normalized to  $1 \times 10^6$ ) and IVS FS data (non-normalized) will use the background subtracted values for analysis.

Listings will include actual value and absolute and fold-change from baseline and response status according to Method 1 (Section 2.1).

### 2.1.3. Dextramer

The frequency (%) of antigen-specific CD8 T-cells will be assessed using ex vivo and IVS dextramer based assays. Results will be presented by timepoint, dose-level, and dextramer.

## 2.2. ctDNA

ctDNA response is defined as the absence or reduction of circulating tumor DNA post-baseline. Analysis of ctDNA will be based on results from two laboratories and will be performed separately.

Duration of response is defined as the time in weeks from reduction until the date of increase or presence of ctDNA.

Any patient with detectable ctDNA at baseline whose post-baseline result is less than the baseline value or undetectable will be considered a responder. The number and percentage of responders will be reported.

Doubling will be calculated as the number of weeks between visits where ctDNA first doubles.

Doubling time and response will be based on the tumor molecules per mL (MTM/mL) and Variant Allele Frequency (VAF).

ctDNA levels over time will be summarized using descriptive statistics.

Data listings will present ctDNA values (VAF and MTM/mL) over time, ctDNA response, and duration of response, and time until doubling of ctDNA.

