### **13.3.3.3. Analysis of Duration of Biomarker Response**

Duration of biomarker response (ie, reduction or clearance) will be reported for subjects who meet the biomarker reduction or clearance definitions.

- Duration of biomarker reduction is calculated from the date of the first biomarker blood test with a reduction compared to baseline, until the earliest date of any of the following events: (1) subsequent increase in biomarker; (2) subsequent disease recurrence; or (3) death due to any cause.
- Duration of biomarker clearance is calculated from the date of the first negative ctDNA test or the date when the serum tumor biomarker is  $\leq$ ULN to the earliest date of any of the following events: (1) subsequent positive ctDNA test or subsequent serum tumor biomarker  $>$ ULN; (2) subsequent disease recurrence; or (3) death due to any cause.

If a subject has not experienced any of the events for reduction or clearance, duration of response will be censored on the date of the last biomarker assessment.

Response duration will be summarized for each cohort. Assessment of biomarker response duration is considered supportive of the primary biomarker response analysis and is not considered part of the fixed sequence testing procedure to control overall type 1 error.

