
Clearance
	
Define as the percent change from baseline of the on-study ctDNA, or CA19-9, or CEA that achieved -100%.
 
Notes:
 
 
a. Clearance start will be the date of first clearance.
 
b. Once clearance start date is identified for a biomarker, the same biomarker will be used to determine the clearance end date.
 
c. Results will not be considered if a subject has already started taking subsequent anti-cancer therapy.
 
d. If there is a tie for best response across biomarkers, select ctDNA first.                             
 
▪ For PDAC subjects, select CA19-9 second, CEA third.
 
• For CRC subjects, select CEA second, CA19-9 third.
 
 
 

Reduction
	
Defined as the percent change from baseline of the on-study ctDNA, or CA19-9, or CEA that achieved any decrease (i.e., a negative percent change from baseline).
 
Notes:
 
 
a. Reduction start will be the date of first reduction.
 
b. Once reduction start date is identified for a biomarker, the same biomarker will be used to determine the reduction end date.
 
c. Results will not be considered if a subject has already started taking subsequent anti-cancer therapy.
 
d. If there is a tie for best response across biomarkers, select ctDNA first.                             
 
• For PDAC subjects, select CA19-9 second, CEA third.
 
• For CRC subjects, select CEA second, CA19-9 third.
 
 
 

Duration of Biomarker Clearance/Reduction
	

Clearance Duration
	
This is confirmed after clearance start by an increase above -100% change from baseline followed by a second increase above -100% at least 1 week afterwards.
 
Notes:
 
 
a. The end date will be the date of the first subsequent increase.
 
b. If the increase cannot be confirmed by a second increase, then the potential end date of biomarker clearance will proceed to the next increase and so on.
 
c. Subjects with confirmed clearance duration will not be censored.
 

Reduction Duration
	
This is confirmed after reduction start by an increase above the initial reduction followed by a second increase above the initial reduction at least 1 week afterwards.

**Final Analysis  

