DATE: HH:MM/DDMMYY

Protocol ELI-002-001                      Elicio Therapeutics, Inc.                      Confidential                      Page 1 of x

Table 7  
 Summary and Change from Baseline for ctDNA (ctDNA  
 Population)

Baseline	Baseline (1)	Cohort 1 (N=xx)	Cohort 1 (N=xx)	Cohort 1 (N=xx)
		N (2)	xx	--
		Mean (SD)	xx.x (xx.xx)	
		Median Min,	xx.xx xx.x	
		Max	xx.x	
		N Undetectable (3)	xx.x, xx.x xx	
		<repeat for remaining visits with at least 3 subjects		
Visit 6		N (2)	xx	xx
		Mean (SD)	xx.x (xx.xx)	xx.x (xx.xx)
		Fold Change Mean	xx.xx	xx.xx
		Fold Shange SD- SD	xx.x	xx.x
		Median	xx.x	xx.x
		Min, Max	xx.x, xx.x	xx.x, xx.x
		N Undetectable (3)	xx	xx
Doubling Time	N(4)	Mean (SD)		
		Median		
		Min, Max		
Clearance Duration (weeks)	N(5)	Mean (SD)		
		Median		
		Min, Max		
Response Rate	n%			

[1] Baseline is based on Visit 3 result or Visit 2 if Visit 3 is missing  
 [2] N reflects the number of patients with detectable concentrations of ctDNA .

[3] Number of subjects with results below the limit of detection. [4] N reflects the subjects whose ctDNA doubled.

[5] N reflects subjects whose ctDNA was undetectable or decreased post-baseline.

[REPEAT univariate statistics For VAF + MTM/ML by Assay]

Notes for programming: Timepoints –

- Visits 2, 3 (pre-vaccination)
- Visits 6, 11, 12, 16, 17, 18, 19, 20, 21, 22, 23, 24 (post-vaccination)

Elicio Therapeutics, Inc.  
Protocol ELI-002-001

Confidential

[figure not shown]
Page 1 of x

Figure 1

Ex vivo Fluorospot

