(1) response is defined as decrease from baseline or undetectable value. (2) Duration is calculated as the date of the first response until the date where the ctDNA is detectable or greater than baseline value. (3) Doubling time is the time until the ctDNA has increase 2-fold from nadir.

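### As literally written, the ctDNA addendum ends a response on detectability even for subjects who were reduced but never cleared, in conflict with Protocol 13.3.3.3 and SAP Table 8

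*SAP*

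**What the plan says.** SAP Addendum 2.2 sets a wide definition of response: "ctDNA response is defined as the absence or reduction of circulating tumor DNA post-baseline". The responder rule confirms that a partial fall is enough: "Any patient with detectable ctDNA at baseline whose post-baseline result is less than the baseline value or undetectable will be considered a responder". A responder may therefore still have detectable ctDNA. The same section gives one end rule for all responders: "Duration of response is defined as the time in weeks from reduction until the date of increase or presence of ctDNA".

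Two shells in the addendum carry the merged idea. Listing 7, footnote 2: "Duration is calculated as the date of the first response until the date where the ctDNA is detectable or greater than baseline value". Table 7 has a row for clearance duration in weeks, but its footnote on who is counted reads: "5] N reflects subjects whose ctDNA was undetectable or decreased post-baseline".

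Protocol 13.3.3.3 treats the two kinds of response separately. For reduction, the start is given as: "Duration of biomarker reduction is calculated from the date of the first biomarker blood test with a reduction compared to baseline". The end is the earliest of "1) subsequent increase in biomarker; (2) subsequent disease recurrence; or (3) death due to any cause". Clearance runs from the first negative test to a later positive one, again with recurrence and death as end events. A subject with no end event is censored at the last biomarker assessment.

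SAP Table 8 (section 12.1) also separates the two. It ends a reduction only on "an increase above the initial reduction followed by a second increase above the initial reduction", with the second value at least one week after the first. Clearance ends on a rise confirmed in the same way.

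**The concern.** The end rule in Addendum 2.2 does not say which end event belongs to which kind of response. If it is applied as worded to a subject who was reduced but not cleared, the *presence* condition is already true when the response starts. The response then lasts 0 weeks. If a programmer requires the end to fall after the start, it lasts until the next detectable sample, even when ctDNA is still falling. Neither result measures how long the reduction held.

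Both sets of rules are live. SAP section 14.0 sends ctDNA analyses to the attached addendum, while Table 8 in the same SAP defines ctDNA durations. The addendum is Version 1.0, dated February 6, 2023. The SAP revision history shows duration definitions being added at Version 3.0 in August 2024. Nothing states which text prevails, and section 14.0 does not list the addendum's end rule as a departure from the protocol. Duration of biomarker clearance and reduction is a named exploratory endpoint (Protocol 6.2.3, SAP 9.1.3), so the study report could carry conflicting durations for the same subject.

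**Working it through.** The plan states no figure that depends on this rule, so there is nothing to reproduce. The check applies each documented rule to the same data.

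**Inputs.** Sampling weeks come from Addendum Table 1-1: 0 (baseline), 3, 17, 20, 25, 29, 37 and 49. The ctDNA values are invented for illustration; they are not trial data.

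- Subject A, reduced, always detectable, later rising: 10, 5, 4, 4, 6, 7, 12, 20
- Subject B, reduced, always detectable, never rising: 10, 5, 4, 3, 3, 2, 2, 1
- Subject C, cleared at Week 3, detectable again at Week 25: 10, 0, 0, 0, 2, 3, 4, 12

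**Formula.** Duration = week of end event − week of first response. The first response is at Week 3 in all three. With no end event, the duration is censored at the last sample: 49 − 3 = 46 weeks. Table 8 gives no censoring date, so the protocol's is used for it.

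**Subject A**

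- Addendum 2.2 or Listing 7, literal: the Week 3 value of 5 is detectable, so 3 − 3 = 0 weeks.
- Same wording, but the end must follow the start: the Week 17 value of 4 is detectable, so 17 − 3 = 14 weeks.
- Protocol 13.3.3.3: the first increase is at Week 25 (6, against 4 at the previous sample and 5 at first reduction), so 25 − 3 = 22 weeks.
- Table 8: 6 at Week 25 exceeds the first reduction of 5, and 7 at Week 29 confirms it, so 22 weeks.
- Addendum 2.2 with its terms paired (reduction ends at increase, absence ends at presence): 22 weeks.
- Listing 7 paired in the same way (reduction ends above baseline): the first value above 10 is 12 at Week 37, so 37 − 3 = 34 weeks.

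**Subject B**

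- Literal wording: 0 weeks. Next detectable sample: 14 weeks.
- Protocol 13.3.3.3, Table 8 and both paired readings: no end event, censored at 46 weeks.

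**Subject C**

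- Addendum 2.2 and Listing 7 as worded, Protocol 13.3.3.3 and Table 8: detectable again at Week 25 (confirmed at Week 29 for Table 8), so 25 − 3 = 22 weeks throughout.

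The conflict therefore arises for subjects who are reduced but still detectable, and not for the cleared subject.

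**The case against.** The best defence is that the addendum's two phrases are meant as pairs: reduction ends at increase, and absence ends at presence. On that reading no response has zero length, and Addendum 2.2 agrees with the protocol and Table 8 for Subjects A, B and C. This is plausible as intent, so a reader should not infer that every reduced-but-detectable responder must be given 0 weeks. But the pairing is not stated. The sentence names only reduction as the start and attaches both end events to it. Pairing also leaves the addendum inconsistent with itself, because Listing 7 would wait for a value above baseline (34 weeks for Subject A) where 2.2 would stop at an increase (22 weeks).

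A second defence is that Protocol 6.2.3 and SAP 9.1.3 also merge an increased and a positive biomarker into one end event. That is true, and it means the protocol is not uniformly at odds with the addendum. Those sections do say that the event must be *subsequent*, and Protocol 13.3.3.3 then separates the two cases. The addendum does neither.

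Third, the consequences are limited. The endpoint is exploratory, Protocol 13.3.3.3 calls duration supportive, about 18 subjects are planned, and the addendum describes its interpretation as descriptive. The listings show ctDNA values over time, so durations can be recalculated. All of this stands. It limits the importance of the point but does not settle which duration is reported.

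**Conclusion.** The point holds for the literal wording. Addendum 2.2 and Listing 7 end a response on detectability in subjects who were reduced but never cleared, and Table 7 counts those subjects under clearance. Protocol 13.3.3.3 ends a reduction only at a subsequent increase, recurrence or death; Table 8 requires a confirmed increase.

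In the illustration the literal rule shortens Subject A by 22 weeks (0 against 22), or by 8 weeks (14 against 22) if the next sample is used. Subject B gets 0 or 14 weeks instead of censoring at 46. These sizes rest on invented values at the planned sampling weeks. The documents do not say how many responders will be reduced without clearing, so the overall effect cannot be estimated.

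Two stronger inferences are not supported. One is that the four statements always give four different answers: for Subject B, read literally, they give two. The other is that addendum durations can never match the main SAP: they match for the cleared subject, and in 2.2 they match for reduced subjects on the paired reading. The secondary endpoint, the proportion with reduction or clearance, is unaffected. The correction should be made, but it does not threaten the trial's main conclusions.

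**What to change.** In Addendum 2.2, Table 7 and Listing 7, replace the single duration with two.

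- **Reduction duration:** from the first test below baseline to a subsequent increase, disease recurrence or death, whichever is earliest. Remove the *presence* and *detectable* conditions from this rule.
- **Clearance duration:** from the first negative ctDNA test to a subsequent positive test, recurrence or death, whichever is earliest.
- **Both:** if none of these occurs, censor at the last biomarker assessment, as Protocol 13.3.3.3 does. The addendum now gives no recurrence, death or censoring rule.
- **Table 7:** use separate rows, each with its own count, so that subjects who were only reduced are not reported under clearance.
- **Definition of increase:** use one throughout, either the subsequent increase in Protocol 13.3.3.3 or the confirmed increase in Table 8. This also replaces the above-baseline condition in Listing 7. State that the chosen definition takes precedence over the February 2023 addendum wording. If Table 8 is chosen, record it in SAP section 14.0 as a change from the protocol.

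The cost is SAP wording and a small programming change. No new data are needed, and the sample size and the response-rate analysis stay as they are.

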### **6.7.2. Permanent Stopping Treatment Administration**

If a subject meets any of the following conditions, the subject will be required to discontinue the trial treatment administration but should continue other trial-related procedures as specified for the follow-up period of the study. (See [Section 7.3](#) for more information on procedures for subjects withdrawn from trial treatment.)

1. Evidence of radiographic disease progression
2. Any intolerable AE, at the investigator's discretion

3. During study treatment:
  - Any investigational product use other than ELI-002
  - Other anti-cancer treatment
4. Non-compliance with trial treatments/procedures. If a subject misses  $\geq 2$  trial visits without underlying toxicity, the subject should be re-instructed regarding dosing and follow-up and continue trial participation. If a subject continues to miss trial visits without toxicity and despite re-instruction, they should be discontinued from the trial treatment phase but follow-up data should be collected as possible.
5. The subject requests to be withdrawn from the trial treatment

For subjects whose treatment is discontinued prematurely, the procedures outlined for End of Treatment/Visit 15 (Table 14) will be carried out and, if possible, prior to the initiation of any other anti-cancer treatment. These subjects should then enter the Follow-up Period, where procedures listed in Table 15 and Table 16 will be performed. In the event that a subject will not continue to be evaluated in the Follow-up Period, the End of Study visit (Visit 24) should be scheduled, and all procedures performed.

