## 2.0 REVISION HISTORY

Version/Date	Version name	Section	Changes implemented
Draft Version 0.2, 19Apr2021	Updated draft	N/A	N/A
Draft Version 0.3, 25Aug2021	Updated draft	All	Protocol Amendment 4.0
Draft Version 0.3, 14Dec2021	Updated draft	All	Updates per sponsor comments
Draft Version 0.3, 14Jan2022	Updated draft	All	Updates per sponsor comments
Draft Version 0.3, 31Mar2022	Updated draft	All	Updates per sponsor comments
Draft Version 0.4, 28Apr2022	Updated draft	All	Updates for consistency with mocks
Draft Version 0.5 30Aug2022	Updated draft	All	Updates as per Protocol Version 6.0
Draft Version 0.6 13Oct2022	Updated draft	All	Add clarification for section 8.4.2: the best response will be only be evaluated for neo-adjuvant participants  Add cohorts 4 and 5 per Sponsor's request and approval.
Draft version 0.6 05Dec2022	Updated draft	All	Updates as per Client comments
Draft version 0.6 16Mar2023	Updated draft	7.4	Algorithms on Patient Reported Outcomes are added. Addressed comments from the client.
Version 1.0 14Apr2023	Final		As a part of the exploratory analysis added a summary of TEAE and RFS by tumor types.
Version 2.0 01Aug2023	Draft		SAP Addendum on the Immunogenicity and ctDNA is added as an APPENDIX.
Version 2.1 04 Dec2023	Updated draft		Updates per sponsor comments
Version 3.0 ddAug2024	Updated draft		Updates to add the following changes: 
 
• Tumor biomarker reduction and clearance definitions, and analyses
 
• Duration of biomarker
 

**Final Analysis  
Statistical Analysis Plan (SAP)**

		reduction and clearance definitions, and analyses 
 
• RFS windows and censoring rules
 
• planned analyses following early termination of long-term follow up phase
 

--	--	--

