**Table 8: Derived variables**

Variables	Formula
Demographic and Baseline characteristics	
Body mass index (BMI) (kg/m  )	weight (kg)/[height (m)] 
Derivation of Duration	
Study day at any visit	Date of interest – date of first dose of study treatment. One day is added if this difference is ≥ 0
Duration of study (Days)	(Date of study completion/discontinuation (for discontinued subjects) – date of first dose) + 1
Duration of Exposure to the study treatment ( weeks )	Is [last date of booster dose – first date of immunization dose] + 1] / 7. IF treatment discontinuation, then last date of booster dose = last dose date prior to or at the date of treatment discontinuation.
Treatment Exposure and Compliance	
Cumulative Planned volume (mL)	Total planned volume for each dose* Planned number of doses for the duration of exposure
Cumulative actual volume administered (mL)	Total actual volume administered from exposure CRF page (Cumulative value of 'Actual volume administered' from Study Drug Administration)
Expected Dose	Calculated as the expected number of vaccinations multiplied by assigned dose in mg
Compliance (%)	(Cumulative actual volume administered /Cumulative planned volume)*100
Dose intensity (DI) for ELI-002 Amph-Peptides 2P	Amount of actual cumulative dose of ELI-002 Amph-Peptides 2P (mg) divided by expected dose given for a full 10 course of vaccinations.
Dose intensity (DI) for ELI-002 Amph-CpG-7909	Amount of actual cumulative dose of ELI-002 Amph-CpG-7909 (mg) divided by expected dose given for a full 10 course of vaccinations.
Relative dose intensity	Cumulative dose received divided by expected dose and multiplied by 100
Baseline Derivations	
Baseline value	Unless otherwise specified, the baseline value is defined as the last non-missing observation prior to administration of the first dose of study treatment. For most assessments, this would be the Visit 3 value. If Visit 3 is missing, the Visit 2 value will be used.
Change from baseline	Post baseline value – Baseline value
Fold change from baseline	(Post baseline value – Baseline value)/Baseline value
Biomarker Reduction/Clearance	
Note: All reporting will select the biomarker (ctDNA, CEA, or CA-19) which contains the best (i.e., largest decrease post-baseline) result per subject. If there is no decrease for a given subject, then “best” is the smallest increase.	

**Final Analysis  
Statistical Analysis Plan (SAP)**

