## 14.0 CHANGES TO PLANNED ANALYSIS FROM STUDY PROTOCOL

The protocol has indicated that statistical testing and confidence intervals would be computed for the efficacy analyses; however, since the sample sizes are small and efficacy data from this trial are exploratory and not powered to elicit statistically significant treatment effects, no formal statistical testing will be computed except for RFS and OS endpoints. ctDNA and Immunogenicity analyses are beyond the scope of this document and are specified in a separate addendum which is attached here as an appendix.

Additional exposure outcomes namely Dose Intensity (DI) and Relative Dose Intensity (RDI) not mentioned in the protocol will be summarized for better clarity on the treatment exposure.

The protocol has requested that summary statistics be presented for patient reported outcomes, however, due to the early termination of the long term follow up of the study, only by-subject listing will also be provided for these endpoints.

The protocol has requested the use of the Disease Response Evaluable Set population, however, as no outputs in the SAP/shells are based on this set, it was dropped from the SAP.

**Final Analysis  
Statistical Analysis Plan (SAP)**

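### The SAP holds two conflicting ctDNA response rules: Table 8 drops results after subsequent anti-cancer therapy, but the addendum that reports the ctDNA response rate has no such cut-off

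*SAP*

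**What the plan says.** **Addendum.** Section 2.2 states: "Any patient with detectable ctDNA at baseline whose post-baseline result is less than the baseline value or undetectable will be considered a responder". A footnote to Listing 7 repeats it: "response is defined as decrease from baseline or undetectable value". Section 2.2 asks for the count and percentage of responders, and the Table 7 shell has a response-rate row and a duration row. The ctDNA population (addendum 1.5) is everyone treated who contributes any ctDNA data. Duration runs from the reduction until ctDNA rises or is present, with no censoring rule. None of these places mentions subsequent anti-cancer therapy.

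**SAP body.** Table 8 introduces its biomarker definitions with "All reporting will select the biomarker (ctDNA, CEA, or CA-19) which contains the best (i.e., largest decrease post-baseline) result per subject". Note c, under both clearance and reduction, says: "Results will not be considered if a subject has already started taking subsequent anti-cancer therapy". The revision history lists "Tumor biomarker reduction and clearance definitions, and analyses" among the additions in Version 3.0 (August 2024). The addendum pages carry Version 1.0, 6 February 2023. SAP 14.0 nevertheless says: "ctDNA and Immunogenicity analyses are beyond the scope of this document and are specified in a separate addendum which is attached here as an appendix".

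**Protocol.** Section 13.3.3.2 defines response as any reduction or clearance against baseline, also without a cut-off. Section 6.7.2 says of subjects who stop treatment: "These subjects should then enter the Follow-up Period, where procedures listed in Table 15 and Table 16 will be performed".

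**The concern.** The secondary endpoint is the proportion of subjects with biomarker reduction or clearance, and Protocol 4.6.5 presents such a change as preliminary proof of concept. A fall in ctDNA first seen after another anti-cancer treatment has begun cannot be read as activity of ELI-002. The Table 8 exclusion recognises this. The addendum does not carry it, so a programmer who follows addendum 2.2 literally would count such a fall. The response rate in addendum Table 7 could then include responders whom the SAP's own later definition would reject.

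**Working it through.** The plan states no expected response rate, so there is no figure to reproduce. The check is a comparison of the texts, followed by simple arithmetic.

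**1. The two rules side by side.**

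| | SAP Table 8 | Addendum 2.2, Table 7, Listing 7 |
|---|---|---|
| Version | SAP 3.0, August 2024 | 1.0, 6 February 2023 |
| Marker | Best of ctDNA, CA19-9, CEA | ctDNA only, separately for two laboratories |
| Response | Any decrease; clearance is -100% | Any value below baseline, or undetectable |
| Results after subsequent therapy | Excluded (note c) | Not addressed |

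**2. Which text produces the rate.** SAP Table 15 covers only RFS, OS and 1-year RFS. SAP 13.6 and 13.8.2 describe waterfall and swimmer plots for the biomarkers. In the text supplied, the explicit request for a ctDNA responder percentage is in the addendum. The SAP's table shells are a separate document and were not available.

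**3. Whether such samples can arise.** Addendum Table 7 lists post-baseline Visits 6, 11, 12 and 16 to 24, which is 3 + 9 = 12 visits, 9 of them in follow-up. Protocol 6.7.2 gives progression and other anti-cancer treatment as reasons to stop ELI-002, and sends those subjects into follow-up. Protocol Table 15 draws ctDNA at each of Visits 16 to 24. SAP 13.4.2 plans a summary of subsequent cancer therapies, so the plan expects them.

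**4. Direction for the response rate.** Let r be the responders on samples before subsequent therapy, m the subjects whose first fall comes only after it, and n the denominator. The rate is r/n with the cut-off and (r + m)/n without it. The difference is m/n, which cannot be negative. The denominator does not change, because a subject with a baseline sample is already in the ctDNA population.

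**5. Size per misattributed subject.** Cohorts have 3 to 6 subjects and about 18 are planned in total (Protocol 13.1).

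| m | n = 18 | n = 6 | n = 3 |
|---|---|---|---|
| 1 | 1/18 = 5.6 points | 1/6 = 16.7 points | 1/3 = 33.3 points |
| 2 | 2/18 = 11.1 points | 2/6 = 33.3 points | 2/3 = 66.7 points |

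The documents do not give m. Because the addendum analyses the two laboratories separately, n for one assay can be smaller than the cohort.

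**6. Direction for duration.** A subject who responded before the new therapy and whose ctDNA stays low on it gets a longer duration. A subject whose first fall comes on the new therapy adds a new duration of unknown length, which may be short and lower the mean or median. The net sign is not determined.

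**The case against.** The strongest reply is that the SAP has already dealt with this. Table 8 is the later text, its introductory note covers all reporting and names ctDNA, and note c excludes these results. SAP 9.1.3 and 13.8.2 place only immunogenicity outside the SAP; section 14.0 alone adds ctDNA. The addendum rule agrees with Protocol 13.3.3.2, and the analyses are descriptive. Much of this stands: biomarker reporting under the SAP body is protected, and the addendum is silent on later therapy, which is different from saying that such values count. But section 14.0 is explicit, the addendum remains attached with its own rule, and no text ranks the two.

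Four stronger readings are tempting, and the documents do not support them.

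- A reader might infer that the plan credits a response to later chemotherapy to ELI-002. It does not say so, and Table 8 rejects it. The addendum allows it by omission.
- A reader might infer a large effect from the 5-month median RFS in Protocol 4.6.4. Visit 16 is Day 231 - Day 57 = 174 days, or 174/30.4375 = 5.72 months, after dose 1. An exponential assumption gives 1 - 2^(-5.72/5) = 55% relapsed by then. That median is for resected pancreatic cancer with persistent postoperative ctDNA, while the trial enrols several tumour types. The 10.4-month median in Protocol 4.1.1, for raised CA19-9 after adjuvant chemotherapy, gives 1 - 2^(-5.72/10.4) = 32%. Relapse is also not the start of new therapy: Protocol 6.1.2 lets some subjects continue ELI-002 after unconfirmed progression. The SAP further records early termination of long-term follow-up, so the number of late samples is unknown.
- A reader might infer that durations are always lengthened. Step 6 shows otherwise.
- A reader might take any difference between the SAP-body and addendum rates as proof of this defect. The two differ by design, since one takes the best of several markers and the other uses ctDNA alone.

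**Conclusion.** The inconsistency is real and worth correcting. One SAP contains two ctDNA response rules, and section 14.0 assigns ctDNA to the older one, which lacks the exclusion. Followed as written, addendum Table 7 can only overstate the response rate relative to Table 8 note c: by 17 points per affected subject with n=6 and by 33 points with n=3. These are sizes per subject, not a forecast. They rest on the planned cohort sizes and on at least one subject having a first ctDNA fall after starting other therapy. Subjects whose ctDNA had already fallen before that therapy are responders under either rule and do not change the rate.

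**What to change.** In addendum 2.2, the Table 7 response-rate and duration rows, and Listings 7 and 8, apply Table 8 note c: only ctDNA results dated before the start of subsequent anti-cancer therapy count for response and duration. Censor a response still ongoing at that point at the last ctDNA sample before the therapy. A date filter alone is not enough, because the addendum has no censoring rule and such a response would have no end date. Show later values in the listings with a flag.

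Leave the by-visit ctDNA level summaries unfiltered, or present them both ways. Note c covers only clearance and reduction. Removing values after new therapy from the visit means would tend to leave subjects who are still relapse-free, so late means could look better through informative missingness.

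The change is a few sentences, a date filter and a censoring flag. The therapy start date is already needed for RFS censoring in SAP Table 16. The price is fewer usable late samples and more censored durations. The mean and range in the Table 7 shell do not handle censoring, so durations would need a Kaplan-Meier summary or censoring marks in the listing.
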